6.14.4.11. Symptoms of Depression (QIDS-SR16)

The Quick Inventory of Depressive Symptomatology Self-Rated (QIDS-SR16) is a 16-item, self-report instrument intended to assess the existence and severity of symptoms of depression as listed in the American Psychiatric Association's Diagnostic and Statistical Manual of Mental Disorders, 4th Edition (DSM-IV; APA 1994). Patients are asked to consider each statement as it relates to the way they have felt for the past 7 days. There is a unique 4-point ordinal scale for each item with scores ranging from 0 to 3 reflecting increasing depressive symptoms as the item score increases. Additional information and the QIDS-SR16 questions may be found on the University of Pittsburgh Epidemiology Data Center web site (<http://www.ids-qids.org/index.html>). A key reference for this instrument covers its psychometric properties for use in patients with chronic major depression (Rush et al. 2003).

The QIDS-SR16 total score is derived as the sum of the scores across the 9 scale domains. For scale domains that contain more than 1 item, the domain score is the highest item rating given across the items within that domain):

- Sleep: the highest score on any one of the 4 sleep items (Items 1 to 4)
- Depressed mood (Item 5)
- Weight/appetite change: the highest score on any one of the 4 weight items (Items 6 to 9)
- Psychomotor changes: the highest score on either of the 2 psychomotor items (Items 15 and 16)
- Concentration (Item 10)
- Worthlessness/guilt (Item 11)

- Suicidal ideation (Item 12)
- Decreased interest (Item 13)
- Decreased energy (Item 14)

In the presence of missing data, the following rules will be employed to derive the total score. First, considering the 3 multi-item domains (sleep, weight/appetite change, psychomotor change), the domain score should be based on the maximum value across the appropriate items, and it should be missing only if each item is missing. Further, considering the 9 domain scores, the total score should be derived as missing if there are 3 or more domains that are missing; if 1 or 2 domain scores are missing, then the total score should be derived using a total score that is pro-rated to the full scale range (0 to 27) based on the available domain scores, retaining 1 decimal place in the total score derived in the presence of missing data.

The QIDS-SR₁₆ total scores will also be categorized in the following severity classes as shown in [Table 6-8](#).

Table 6-8. QIDS-SR₁₆ Severity of Depressive Symptoms Categories based on the QIDS-SR₁₆ Total Score

QIDS-SR ₁₆ Severity of Depressive Symptoms Category	QIDS-SR ₁₆ Total Score
0=None	0-5
1=Mild	6-10
2=Moderate	11-15
3=Severe	16-20
4=Very Severe	21-27

Abbreviations: QIDS-SR₁₆ = Quick Inventory of Depressive Symptomatology Self-Rated-16.

Treatment differences in mean change in the QIDS-SR₁₆ total score may be analyzed by time point using an ANCOVA model with explanatory terms for treatment and the baseline value as a covariate. Treatment comparisons will be provided showing the LS means for each treatment, the treatment differences in LS means, the 95% CI for treatment differences, within-treatment p-values, and p-values for the treatment differences obtained from the model. Summary statistics for percent change from baseline will also be presented. Missing data will be imputed using mLOCF imputation.

Using the QIDS-SR₁₆ Severity of Depressive Symptoms Categories shown in [Table 6-8](#), shift tables will show the number and percent of patients with total score in each category based on baseline to maximum category during the treatment period, with baseline depicted by the most extreme category during the baseline period, with further summarization of change from baseline in severity using categories of any improvement, no change, and any worsening, by treatment. Similarly, shift tables will be created for the QIDS-SR₁₆ suicidal ideation item (Item 12)

responses. Treatment differences for the shift table summary categorizations will be assessed with the Likelihood Ratio Chi-Square test, using the exact version of this test whenever at least 1 cell has an expected cell count <5 . Scheduled and unscheduled measurements will be included in these analyses. Furthermore, a summary of increases by each maximum severity category will be provided.

In addition, the number and percent of patients with total score in each category based on baseline to each scheduled visit, with baseline depicted by the last category during the baseline period, will be further summarized in terms of shift tables by time point and last visit and by treatment group. Following the shift table for the last visit, a shift table summary of the last visit will be included. Furthermore, a summary of increases by each category at last visit will be provided. Similarly, shift tables will be created for the QIDS-SR₁₆ suicidal ideation item (Item 12) responses by time point, including last visit.

Shift tables for the QIDS-SR₁₆ total score severity categories and for the suicidal ideation item descriptively comparing baseline to maximum and last post-treatment follow-up and follow-up baseline to maximum and last post-treatment follow-up by treatment group will be performed. A shift table summary for each analysis will also be included. Furthermore, a summary of increases by each maximum and last severity category will be provided.

First shift table summary:

- Decreased; maximum post-treatment follow-up category $<$ baseline category
- Increased; maximum post-treatment follow-up category $>$ baseline category
- Same; maximum post-treatment follow-up category $=$ baseline category

Second shift table summary:

- Decreased; maximum post-treatment follow-up category $<$ follow-up baseline category
- Increased; maximum post-treatment follow-up category $>$ follow-up baseline category
- Same; maximum post-treatment follow-up category $=$ follow-up baseline category

Third shift table summary:

- Decreased; last post-treatment follow-up category $<$ baseline category
- Increased; last post-treatment follow-up category $>$ baseline category
- Same; last post-treatment follow-up category $=$ baseline category

Fourth shift table summary:

- Decreased; last post-treatment follow-up category $<$ follow-up baseline category
- Increased; last post-treatment follow-up category $>$ follow-up baseline category
- Same; last post-treatment follow-up category $=$ follow-up baseline category

6.14.5. Study Drug Interruption

A summary of temporary interruptions of study drug will be provided, showing the number of patients who experienced at least 1 temporary interruption and the number of temporary interruptions per patient. Further, the duration of each temporary interruption (in days) and the

cumulative duration of dose interruption (in days) using basic descriptive statistics (n, mean, SD, minimum, median, and maximum) will be displayed.

6.15. Subgroup Analyses

Subgroup analyses comparing baricitinib to placebo will be performed on the mITT population using ACR20, ACR50, DAS28-hsCRP <2.6 , DAS28-hsCRP ≤ 3.2 , SDAI ≤ 3.3 , HAQ-DI Improvement ≥ 0.22 , and change from baseline in HAQ-DI and DAS28-hsCRP at Week 12 (Visit 7) and Week 24 (Visit 11) and using mTSS at Week 24 (Visit 11).

The following subgroups (but not limited to only these) will be categorized into disease-related characteristics and demographic characteristics and will be evaluated:

- Gender (Male, Female)
- Age (<65 years, ≥ 65 years)
- Country
- Screening renal function status: impaired (eGFR <60 mL/min/1.73 m 2) or not impaired (eGFR ≥ 60 mL/min/1.73 m 2)
- Joint erosion status (1-2 joint erosions plus seropositivity, at least 3 joint erosions)
- Background therapy (MTX only, MTX + other cDMARDs)
- Baseline weight (\leq median, $>$ median)
- Baseline BMI category (\leq median, $>$ median)
- Baseline BMI category (<18.5 kg/m 2 , ≥ 18.5 to <25 kg/m 2 , ≥ 25 to <30 kg/m 2 , ≥ 30 kg/m 2)
- Baseline disease severity (DAS28-hsCRP ≤ 5.1 , DAS28-hsCRP > 5.1)

The subgroup analyses for categorical outcomes will be performed using logistic regression. The model will include the categorical outcome based on NRI as the dependent variable and treatment, subgroup, and treatment-by-subgroup interaction as explanatory variables. The treatment-by-subgroup interaction comparing treatment groups will be tested at the 0.1 significance level. The p-value from the logistic regression will be reported for the interaction test. When logistic regression sample size requirements (<5 responders in any category for any subgroup) are not met, the p-value will not be produced. Counts, percentages, the odds ratio, and the 95% CI of the odds ratio within a subgroup obtained from the same model with the subgroup and interaction terms removed will be presented for comparing treatment group differences. For significant findings, further analytical inspection will be made to assess the plausibility of any impact on drug effect.

An ANCOVA will be used to analyze the change from baseline based on mBOCF in HAQ-DI and DAS28-hsCRP at Week 12 and at Week 24, and based on linear extrapolation in mTSS at Week 24 with baseline, treatment, subgroup, and treatment-by-subgroup as explanatory variables. The treatment-by-subgroup interaction will be tested at the 0.1 significance level. The LS mean, LS mean difference, SE, and 95% CI within subgroups obtained from the same ANCOVA model with the interaction and subgroup terms removed will be presented.

Descriptive statistics will be provided for each treatment and stratum of a subgroup as outlined, regardless of sample size. In addition, the aforementioned formal statistical analysis will be performed when there are a minimum of 30 patients per treatment group per stratum of the subgroup. In some cases, select strata within the subgroups may need to be pooled in order to

achieve 30 patients per treatment group per stratum for analysis. The descriptive and analysis statistics for the pooled strata will be displayed in addition to the descriptive statistics for the initial strata. The detailed pooling strategy is described below:

- For subgroups with 2 strata: gender, age, screening renal function status, background therapy, joint erosion status, baseline weight, baseline BMI category, baseline disease severity (DAS28-hsCRP) —If 1 of the strata fails to meet the required minimum number, then no formal statistical analysis will be provided.
- Country (3 strata)—Pool patients from Argentina and Brazil if needed. If after pooling, 1 of the strata fails to meet the required minimum number, then no formal statistical analysis will be provided.
- Baseline body mass index (four strata) —If one of the strata fails to meet the required minimum number, the stratum will be pooled with the next contiguous heavier BMI stratum, except for the heaviest BMI stratum which will be pooled with the next heaviest BMI stratum. The pooling will continue until all strata including pooled strata meet the required minimum number.

6.16. Exploratory Analysis

- Comparison between baricitinib and placebo in change from baseline to Weeks 16, 24, and 52 in mTSS: The actual scores and change from baseline scores at Week 16, 24, and 52 in mTSS will be summarized. An ANCOVA model with baseline score, country/region, baseline joint erosion status, and treatment group in the model will be used to test the treatment difference between baricitinib and placebo in change from baseline to Week 24 in mTSS scores. Type III sums of squares for the LS means will be used for the statistical comparison; 95% CI will also be reported. The LS mean difference, SE, CI, and p-value will be presented. The linear extrapolation method described in Section 6.3 will be used. The LOCF approach described in Section 6.3 will be used as a sensitivity approach to the linear extrapolation method to impute missing data.

Supportive analyses using the cumulative responder curves, in which patients who have discontinued their randomized treatment are defined as progressors across the spectrum of choices of analysis thresholds will be provided.

- Descriptive statistics for the proportion of patients with mTSS change ≤ 0 by treatment group at Weeks 16, 24, and 52 will be provided by visit and treatment group. Logistic regression will be conducted to analyze the proportion of patients with mTSS change ≤ 0 at Weeks 16, 24, and 52 between baricitinib and placebo. The model for the logistic regression will consist of county/region, baseline joint erosion status, and treatment as fixed effects. Summaries by treatment group will be provided for the proportion of patients who improved or experienced no change (mTSS ≤ 0), or worsened (mTSS > 0).

In addition, the proportion of patients with change in mTSS $\leq SDC$ and mTSS ≤ 0.5 at Weeks 16, 24, and 52 will be analyzed in a similar manner as described for mTSS change ≤ 0 . The SDCs at Weeks 16, 24, and 52 are defined as the smallest detectable change which is

computed from the variability in Week 0 to Week 16, Week 24, or Week 52 change in scores assigned by the blinded imaging assessors, respectively (Bruynesteyn 2005).

The linear extrapolation method described in Section 6.3 will be used to impute missing data. The categorical analyses described above will be applied to the mITT population, and a subset of mITT population that includes all randomized patients who received at least 1 dose of study drug, have non-missing baseline and at least 1 non-missing postbaseline mTSS measurement.

- Descriptive statistics for the actual score and change from baseline scores at Week 16, Week 24, and Week 52 in joint space narrowing and in bone erosion scores will be provided by visit and treatment group.
- Descriptive statistics for the proportion of patients achieving ACR20, ACR50, and ACR70 at each postbaseline visit through Visit 15 (Week 52) will be provided by visit and treatment group. A logistic regression with the same model specification as the primary analysis will be used for the treatment comparisons through Week 24 for ACR20, ACR50, and ACR70. The observed (“as-is”) values of the ACR20, ACR50, and ACR70 will be summarized as a sensitivity approach to the primary method of NRI. Using the “as-is” approach, the ACR values are calculated without applying any imputation to the components.
- Descriptive statistics for the proportion of patients achieving EULAR Responder Index based on the 28-joint count at each postbaseline visit will be provided by visit and treatment group. EULAR nonresponders and responders (moderate + good responders) will be summarized. The NRI method will be used as the missing data imputation technique. A logistic regression analysis will be performed to compare the proportion of EULAR responders between baricitinib and placebo through Week 24. The model will consist of country/region, baseline joint erosion status, and treatment as fixed effects. The analysis will be repeated to compare the treatment groups in proportion of patients achieving good responses. Apart from the aforementioned categories, a summary table with frequencies and percentages will be presented for the patients categorized as good responder, moderate responder, and nonresponder. The observed values will be analyzed as a sensitivity approach to the primary method that utilizes NRI.
- A logistic regression analysis will be conducted to analyze the patients with specified categories up to Week 24 as below. The model for the logistic regression will consist of country/region, baseline joint erosion status, and treatment as fixed effects to compare baricitinib to placebo. Besides, descriptive statistics will be provided by visit and by treatment group for the following endpoints.
 - The proportion of patients achieving DAS28-ESR ≤ 3.2 and < 2.6 and DAS28-hsCRP ≤ 3.2 and < 2.6 at post-baseline visits.
 - The proportion of patients achieving HAQ-DI improvement from baseline ≥ 0.22 and ≥ 0.3
 - The proportion of patients achieving SDAI score ≤ 3.3 (ACR/EULAR remission index-based definition) and CDAI score ≤ 2.8 up to Week 52; the proportion of patients achieving CDAI score ≤ 10 and proportion of patients achieving SDAI score ≤ 11 up to Week 52.
 - The proportion of patients achieving ACR/EULAR remission according to the Boolean-based definition by treatment group.

- Change from baseline to postbaseline visits up to Week 24 in specific endpoints will be analyzed using an ANCOVA model with treatment, country/region, baseline joint erosion status, and baseline score in the model to test the treatment difference between baricitinib and placebo.
Besides, descriptive statistics will be provided by visit and by treatment group for the following endpoints. The mLOCF approach described in Section 6.3.1 will be used to impute missing data.
 - The percent change from baseline and change from baseline in individual components of the ACR core set, including TJC68, SJC66, patient's assessment of arthritis pain, Patient's Global Assessment of Disease Activity, Physician's Global Assessment of Disease Activity, and hsCRP at postbaseline visits.
 - The actual score and the change in DAS28-hsCRP and in DAS28-ESR from baseline to post-baseline visits.
 - The actual score and the change in HAQ-DI from baseline to post-baseline visits.
 - The actual score and the change in CDAI and in SDAI from baseline to post-baseline.
- Descriptive statistics for the hybrid ACR (bounded) response at all postbaseline visits will be provided by visit and treatment group. An ANOVA model with country/region, baseline joint erosion status, and treatment group as fixed effects and the postbaseline hybrid ACR response as the dependent variable will be used to compare baricitinib to placebo through Week 24. The mLOCF approach described in Section 6.3.1 will be used to impute missing data

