The Safety Assessor (or designee) should be a rheumatologist (or medically qualified physician) and will have access to both safety and efficacy data. The Safety Assessor may be the Principal Investigator (PI). The Safety Assessor will be responsible for completing the Physician’s Global Assessment of Disease Activity (VAS). To ensure consistent Physician’s Global Assessment of Disease Activity (VAS) throughout the trial, the instrument should be evaluated by the same physician at all study visits. The Safety Assessor will have access to source documents, laboratory results, and case report forms (CRFs) and will be responsible for making treatment decisions based on a patient’s clinical response and laboratory parameters.

All patients in Study JAGS will be offered rescue therapy starting at Week 16 in line with precedent from recent clinical trials. Patients who are determined to be nonresponders to their originally assigned treatment will be reassigned to treatment with baricitinib at Week 16. Patients originally assigned to baricitinib will be rescued to the same dose of baricitinib to maintain the study blind. Patients not rescued at Week 16 may be rescued to treatment with baricitinib at the discretion of the investigator anytime thereafter. Patients initially randomized to placebo and not rescued will be reassigned to receive baricitinib at Week 24 to limit exposure to inactive treatment. Patients not experiencing improvement in signs and symptoms following approximately 4 weeks of rescue treatment should be discontinued from the study. Patients may be rescued only once. See Section [9.5.1](#) for details of rescue treatment.

8. Study Population

The study population will be comprised of patients diagnosed with RA with active disease who have failed to adequately respond to MTX. Study investigator(s) will review patient records and screening test results to determine that the patient meets all inclusion and exclusion criteria to qualify for participation in the study.

Individuals who do not meet the criteria for participation in this study (screen failure) may be re-screened. Individuals may be re-screened up to 1 time. The interval between re-screenings should be approximately 30 days. Each time re-screening is performed, the individual must sign a new informed consent form (ICF) and will be assigned a new identification number.

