9.5.1. Special Treatment Considerations

In consideration of the disease severity, all patients in Study JAGS will be offered rescue therapy starting at Week 16 if they are determined to be nonresponders.

All patients who are non-responders (in both baricitinib and placebo arm) will receive rescue therapy at Week 16. Patients who are nonresponders and who were randomized to placebo will be rescued with baricitinib. To maintain study integrity through investigational product blinding, patients who were originally randomized to baricitinib will continue to receive baricitinib, with appropriate ongoing assessment of response and use of concomitant medication as needed.

Nonresponse at Week 16 is defined as lack of improvement of at least 20% in both TJC and SJC at both Week 14 and Week 16 compared to baseline. At Week 16, the IWRS will assign rescue treatment based on TJC and SJC values.

After Week 16, rescue therapy will be offered to patients at the discretion of the investigator based on TJCs and SJCs. Once a patient has been rescued, new NSAIDs, corticosteroids, and/or analgesics may be added or doses of ongoing concomitant NSAIDs, corticosteroids, and/or analgesics may be increased at the discretion of the investigator.

A patient may only be rescued once. If a patient continues to meet nonresponse criteria for 4 weeks after rescue or at any time point thereafter, that patient should be discontinued from the study.

Nonresponders who are rescued will receive an oral tablet daily for the remainder of the study. Rescue therapy will be administered through Week 52.

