5.1.1. Screening Period

This is a screening period of not less than 3 days and not more than 42 days. In exceptional circumstances, the screening window can be extended after consultation with the Sponsor. Patients will be screened for study eligibility at Visit 1 and will be randomized at Visit 2 to continue in Part A.

5.1.2. Parts A and B: 24-Week Double-Blind Placebo-Controlled (Part A) Period and 28-Week Open-Label (Part B) Period

Patients on a background of MTX will be randomized at a 1:1 ratio to 1 of 2 treatment arms (baricitinib or placebo):

- Patients randomized to baricitinib will be administered a 4-mg tablet QD (or 2 mg baricitinib tablet QD if eGFR <60 mL/min/1.73 m²) starting at Week 0 (Visit 2) through Week 52 (Visit 15).
- Patients randomized to placebo will be administered a placebo tablet QD starting at Week 0 (Visit 2) through Week 24 (the morning of Visit 11). At Week 24, patients will be administered baricitinib 4 mg QD (or 2 mg baricitinib QD if eGFR <60 mL/min/1.73 m²)

through Week 52 (Visit 15). Patients will be eligible for rescue treatment beginning at Week 16 (Visit 9). Details of the rescue are listed in Section 5.3.3.

Patients will remain on background MTX, nonsteroidal anti-inflammatory drugs (NSAIDs), analgesics, and/or corticosteroids (see Protocol Section 9.8 for guidelines on adjustments to concomitant therapy). Patients will take their assigned doses of study drugs as directed. The primary efficacy endpoint will be at Week 12, and the final visit during Part A will be at Week 24. The final visit during Part B will be at Week 52 (Visit 15). The structural joint damage endpoints will be obtained at Weeks 16, 24, and 52. All patients who complete the Week 52 study visit will be eligible for inclusion in the extension Study JADY.

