Each patient will receive blinded study drug (baricitinib 4 mg or baricitinib placebo tablets orally QD) beginning on the day of Visit 2 (Week 0). Baricitinib 4-mg oral dosing will continue daily through Visit 15 (Week 52). Baricitinib placebo oral dosing will continue daily through Visit 11 (Week 24); at Visit 11 (Week 24), all patients randomized to placebo will be reassigned to baricitinib.

Oral study drug should be taken at home at approximately the same time each day, as much as possible:

- At Visit 2 (Week 0), patients will take their study drug in the clinic.

5.3.3. *Rescue Therapy*

In consideration of the disease severity, all patients in Study JAGS will be offered rescue therapy starting at Week 16 if they are determined to be nonresponders. Nonresponse at Week 16 is defined as lack of improvement of at least 20% in both tender joint counts (TJCs) and swollen joint counts (SJCcs) at both Week 14 and Week 16 compared to baseline. At Week 16, the IWRS will assign rescue treatment based on TJC and SJC values.

All patients who are non-responders (in both baricitinib and placebo arm) will receive rescue therapy at Week 16. Patients who are nonresponders and who were randomized to placebo will

be rescued with baricitinib 4 mg. To maintain study integrity through study drug blinding, patients who were originally randomized to baricitinib will continue to receive baricitinib, with appropriate ongoing assessment of response and use of concomitant medication as needed.

After Week 16, rescue therapy will be offered to patients at the discretion of the investigator based on TJC_s and SJC_s. Once a patient has been rescued, new NSAIDs, corticosteroids, and/or analgesics may be added or doses of ongoing concomitant NSAIDs, corticosteroids, and/or analgesics may be increased at the discretion of the investigator.

A patient may only be rescued once. If a patient continues to meet nonresponse criteria for 4 weeks after rescue or at any time point thereafter, that patient should be discontinued from the study.

Patients initially randomized to placebo and not rescued before Week 24 will be reassigned to receive baricitinib 4 mg at Week 24 in order to limit exposure to inactive treatment.

Nonresponders who are rescued will receive an oral tablet daily for the remainder of the study. Rescue therapy will be administered through Week 52.

6. A Priori Statistical Methods

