6.3.2. Missing Data Imputation for the Structural Progression Endpoint (van der Heijde mTSS)

1. Primary method: Linear extrapolation method

The primary approach to the analysis of the structural progression data will be the linear extrapolation method, which assumes that individual patients would continue to accrue structural damage in their joints at the same rate that was observed at their time of last observation. The linear extrapolation method has been established as an appropriate missing data imputation method in other Phase 3 RA trials (Keystone et al. 2004, 2008, 2009; Cohen et al. 2006; Smolen et al. 2008, 2009). The linear extrapolation method will be used for analysis of the structural progression endpoint (van der Heijde mTSS), including bone erosion scores and joint space narrowing, to impute missing data at time points when analyses are conducted (including the analyses at Week 24 and Week 52). For patients who discontinue from the study or for patients who miss a radiograph for any reason, baseline data and the most recent radiographic data prior to discontinuation or prior to the missed radiograph, adjusted for time, will be used for linear extrapolation to impute missing data at subsequent scheduled time points, including the primary analysis at Week 24. For patients who receive rescue therapy starting at Week 16 or at any time point thereafter, baseline data and the most recent radiographic data prior to initiation of rescue therapy, adjusted for time, will be used for linear extrapolation. For patients who discontinue from the study or permanently discontinue the study treatment after receiving rescue therapy, the radiographic data collected prior to initiation of rescue therapy should supersede the data collected before discontinuation.

All patients originally randomized to placebo will be switched to active treatment at Week 24; thus, there will be no observed data for the placebo arm after Week 24. Therefore, baseline data and the most recent radiographic data prior to initiation of the new therapy, adjusted for time, will be used for linear extrapolation at Week 52. Missing postbaseline values will be imputed only if both a baseline value and a postbaseline value from another time point are available, as long as the patient was receiving the same treatment at each applicable time point. Missing postbaseline values will not be imputed using postbaseline data from later time points.

For example:

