- (1) For a baricitinib-treated patient who did not require rescue therapy:
 - Missing data at Week 16 will be extrapolated from baseline and an early discontinuation visit prior to Week 16, if available.
 - Missing data at Week 24 will be extrapolated from baseline and the last available postbaseline value prior to Week 24.
 - Missing data at Week 52 will be extrapolated from baseline and the last available postbaseline value prior to Week 52, if available.
- (2) For a baricitinib- or placebo-treated patient who was rescued at Week 16:
 - Missing data at Weeks 24 or 52 will be extrapolated from baseline and Week 16.
- (3) For a placebo-treated patient who did not require rescue therapy:
 - Missing data at Week 16 will be extrapolated from baseline and an early discontinuation visit prior to Week 16, if available.

- Missing data at Week 24 will be extrapolated from baseline and the last available postbaseline value prior to Week 24.
- Missing data at Week 52 will be extrapolated from baseline and the last available postbaseline value at or prior to Week 24.

2. Other method: Last observation carried forward

A last-observation-carried-forward (LOCF) approach will also be used for the Week 24 analyses of mTSS, bone erosion scores, and joint space narrowing. Data observed at Week 24 will be analyzed according to randomized treatment group regardless of rescue status. Patients with missing data at Week 24, as a result of study discontinuation or unreadable x-rays, will have their data imputed by last postbaseline observation carried forward.

Details of the missing data imputation rules, methods for between-reader adjudication, score derivations, and other details for the bone erosion scores, joint space narrowing scores, and mTSS are provided in [Appendix 2](#) (van der Heijde Modified Total Sharp Score) and [Appendix 4](#).

[Table 6-1](#) summarizes the imputation techniques for the various endpoints.

Table 6-1 **Imputation Techniques for Various Efficacy and Safety Variables**

Endpoint	Imputation Method
ACR 20/50/70 responses, DAS28-hsCRP and DAS28-ESR LDA and remission, EULAR response criteria based on the 28-joint DAS, ACR/EULAR remission according to the Boolean-based definition, HAQ-DI improvement from baseline ≥ 0.22 and ≥ 0.3 , CDAI LDA and remission, and SDAI LDA and remission	NRI
JSN, bone erosion scores, and mTSS	Linear extrapolation method and LOCF
mTSS ≤ 0 , mTSS ≤ 0.5 , and mTSS \leq SDC	NRI
HAQ-DI, DAS28-hsCRP	mBOCF/mLOCF

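### On its plain wording, the progressor rule for the supportive mTSS curves counts rescue in the placebo arm but not in the baricitinib arm

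*SAP*

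**What the plan says.** Section 6.16 of the SAP analyses change in mTSS to Week 24 by ANCOVA with linear extrapolation, and names LOCF as the sensitivity approach. It then adds supportive cumulative responder curves in which "patients who have discontinued their randomized treatment are defined as progressors across the spectrum of choices of analysis thresholds". It does not say what counts as discontinuing randomized treatment, and it gives no time point for the curves. The bullet they sit in summarises mTSS at Weeks 16, 24 and 52.

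Rescue from Week 16 works differently in the two arms:

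- **Placebo** (Protocol 9.5.1): "Patients who are nonresponders and who were randomized to placebo will be rescued with baricitinib".
- **Baricitinib** (Protocol 7.2): "Patients originally assigned to baricitinib will be rescued to the same dose of baricitinib to maintain the study blind". SAP 5.3.3 agrees: "patients who were originally randomized to baricitinib will continue to receive baricitinib".
- **Remaining placebo patients** (SAP 5.3.2): "at Visit 11 (Week 24), all patients randomized to placebo will be reassigned to baricitinib".

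For the main structural analysis, SAP 6.3.2 gives one extrapolation rule for rescue in both arms. Its second example begins "For a baricitinib- or placebo-treated patient who was rescued at Week 16".

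**The concern.** A rule triggered by leaving the randomized drug can be met through rescue in one arm only. Two patients who meet the same nonresponse criterion at Week 16 would be classified differently. The placebo patient becomes a progressor at every threshold, while the baricitinib patient keeps whatever status the mTSS value gives. The curves would then separate in favour of baricitinib even if the drug had no effect on joint damage. A reader shown them as support for the ANCOVA could take that separation for evidence of structural benefit.

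**Working it through.** **Plan's own figure.** The documents give no rate of rescue or of mTSS progression, so there is no stated figure to reproduce on this point. The only power statement (99% for ACR20, 60% v 35%, 144 per arm) recomputes to 99.1% but has no bearing here.

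**How the SAP handles rescue elsewhere**

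| Place in SAP | Rescued placebo | Rescued baricitinib |
|---|---|---|
| 6.1, efficacy analysis groups | data after rescue excluded | data after rescue excluded |
| 6.3.1, NRI | nonresponder after rescue, to Week 24 | nonresponder after rescue |
| 6.3.2, extrapolation example 2 | baseline and Week 16 used | baseline and Week 16 used |
| 6.16, curves, plain wording | progressor at every threshold | not covered |

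Wording matters here. For discontinuation, Section 6.3.1 speaks of permanently stopping the study treatment and gives rescue its own rule. Section 6.16 refers to randomized treatment and has no rescue rule for the curves.

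**Size at Week 24.** Notation:

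- q = share of patients who are non-progressors at a given threshold, assumed equal in both arms (no drug effect on damage) and unrelated to rescue
- r_B, r_P = share rescued before Week 24 on baricitinib and on placebo
- no other discontinuation

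Non-progressors on the curve, and the gap (baricitinib minus placebo):

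- Plain wording: q v q(1 − r_P), so gap = r_P × q
- Rescue counted in both arms: q(1 − r_B) v q(1 − r_P), so gap = (r_P − r_B) × q
- Rescue counted in neither arm: q v q, so gap = 0

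The part due to asymmetry, measured against counting rescue in both arms, is r_P × q − (r_P − r_B) × q = **r_B × q**.

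| r_B | r_P | q | Plain wording | Both arms | Due to asymmetry |
|---|---|---|---|---|---|
| 8% | 20% | 70% | 14.0 | 8.4 | 5.6 |
| 10% | 20% | 70% | 14.0 | 7.0 | 7.0 |
| 5% | 15% | 70% | 10.5 | 7.0 | 3.5 |
| 10% | 10% | 70% | 7.0 | 0.0 | 7.0 |

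Gaps are in percentage points. Over r_B = 5% to 30% and q = 60% to 80%, r_B × q runs from 0.05 × 0.60 = 3.0 to 0.30 × 0.80 = 24.0 points. If rescued baricitinib patients progress more often than others, q should be replaced by the non-progressor share among those patients. At 50%, for example, 8% rescue adds 0.08 × 0.50 = 4.0 points.

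For scale, take equal 10% rescue in both arms, no drug effect, 144 per arm and q = 60% to 80%. An unadjusted two-sided 5% test at one threshold would then favour baricitinib with probability 0.18 to 0.35. The SAP plans no such test on the curves.

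**Week 16.** Rescue is only assigned at this visit, so the curve is essentially unaffected.

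**Week 52.** SAP 6.3.2 states "All patients originally randomized to placebo will be switched to active treatment at Week 24". On the plain wording every placebo patient has by then left randomized treatment. Placebo non-progressors are 0% at every threshold, and the gap is the whole baricitinib proportion.

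**The case against.** The strongest reply is that the rule is ambiguous, so no bias has been shown. Two other readings treat the arms alike at Week 24:

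- **Rescue counts in neither arm.** Section 6.3.2 speaks of patients who stop study treatment after receiving rescue, so rescue is not itself discontinuation.
- **Rescue ends randomized treatment in both arms.** The Section 6.1 analysis groups drop post-rescue baricitinib data although the drug is unchanged.

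This stands as far as it goes. A reader might infer that the curves favour baricitinib by construction. The documents do not support that, because the SAP never says that rescue counts in one arm and not the other. But neither symmetric reading is written for the curves. The second would also require saying that a patient who continues on baricitinib has discontinued it.

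Four further limits also stand:

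- The planned switch does not affect Week 24 status, because placebo is taken up to the morning of that visit.
- A Week 52 curve is possible but not stated. The sentence follows the Week 24 ANCOVA, and Section 6.11 confines formal comparisons to Week 24 or earlier.
- The SAP does not present the curves as the check on linear extrapolation. LOCF has that role, using observed Week 24 data regardless of rescue.
- Structural progression is an exploratory objective, and no test or decision rests on the curves.

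One could also argue that NRI, which Table 6-1 assigns to the fixed mTSS thresholds, already makes rescued baricitinib patients nonresponders. But Section 6.16 says linear extrapolation is used for those same categorical analyses. The same rescued baricitinib patient could be a non-progressor on the curve and a nonresponder in the table at the same threshold.

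**Conclusion.** The point holds on the plain wording of Section 6.16, which departs from how the SAP treats rescue everywhere else. On that reading the asymmetry adds r_B × q to the Week 24 gap in favour of baricitinib: 5.6 points at 8% rescue and 70% non-progressors, 7.0 points at 10%. These rates are assumptions, as is independence of rescue and progression.

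A reader might attribute the whole 14-point gap in the 20% v 8% example to the asymmetry. That would be wrong: 8.4 of those points come from different rescue rates and remain under any rule that counts rescue as progression in both arms. A zero gap under such a rule requires equal rescue rates.

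If a Week 52 curve is drawn, it carries no comparative information on this reading. The primary and secondary endpoints and the mTSS ANCOVA are unaffected. The correction is worth making before unblinding, but it does not threaten the trial's main conclusions.

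**What to change.** In SAP Section 6.16, replace the progressor rule with:

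*Patients in either arm who, before the analysis visit, discontinued the study, permanently discontinued study drug, or received rescue are defined as progressors.*

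This follows the SAP's own NRI logic. Counting rescue in neither arm would also be symmetric, but it would be a different analysis, so the choice must be written down.

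Two additions:

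- State that the comparative curves are for Week 24, with no placebo comparison at Week 52.
- Reconcile Table 6-1 (NRI) with Section 6.16 (linear extrapolation) for mTSS change ≤ 0, ≤ 0.5 and ≤ SDC, so that the table and the curve agree at the same threshold.

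The cost is a few sentences. Rescue is already recorded, and trial conduct does not change. SAP Section 7 defers x-ray analysis and unblinding to the final lock, so the text can be settled before then. The downside is a slightly lower baricitinib curve. A gap from genuinely different rescue rates will remain, and a note under the figure should say so.
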